Cardiovascular disease (CVD) accounts for one third of all deaths, making it the leading cause of death worldwide (Roth et al 2015). The vast majority (71%) of CVD-related deaths occur in low- and middle-income countries (LMICs), where the number of such deaths increased by two thirds between 1990 and 2013 (ibid). Over this period, the CVD attributable death rate declined by 43% in high-income countries but by only 13% in LMICs. The proportion of total deaths that are caused by CVD is falling in high-income countries but rising in LMICs.

The high and growing number of CVD deaths in low- and middle-income countries is not due to greater exposure to risk factors. The Prospective Urban Rural Epidemiology (PURE) study has demonstrated that while low-income countries have a lower CVD risk-factor burden than high-income countries, they have higher rates of major cardiovascular disease and CVD-related death (Yusuf et al 2014). Deficiencies in prevention and control of disease for given exposure to CVD risks result in a great deal of avoidable mortality in the developing world.

There is a lack of awareness and control of CVD risks worldwide that is most severe in LMICs. The PURE study documents low awareness, medication and control of hypertension (Chow et al, 2013)¹. Such gaps are indicative of more general deficiencies in information regarding exposure to CVD risks and ability to influence these risks through lifestyle and medication. But the gaps are also attributable to deficiencies in healthcare systems. Primary care in LMICs is often focussed on maternal and child services and has tended not to engage in systematic primary prevention of CVD. Consequently, access and affordability of diagnostic testing and medication may be lacking for the minority of individuals who do have some awareness of potential exposure to CVD risk factors.

International agencies are assisting national governments in their efforts to address these problems. The World Health Organization (WHO) Essential Package of Non-Communicable Disease (NCD) Interventions for Primary Health Care in Low Resource Settings (PEN) provides a template for improved prevention, detection and management of chronic illness (WHO 2010). Even more specific to CVD, the WHO, in collaboration with United States (US) Centers for Disease Control and Prevention (CDC) and international medical associations, has recently launched the Global Hearts Initiative. This includes the HEARTS (WHO 2016) package that aims to strengthen management of CVD in primary care largely through implementation of the treatment protocols and risk-based management approach set out in the PEN. Both packages advocate classifying and managing patients on the basis of a global CVD risk score, as opposed to a single risk factor approach.²

The PEN has been widely adopted in LMICs. Given the very low level of primary prevention of CVD in many countries, the package certainly has the potential to make an important impact on population health. But there are reasons for only cautious optimism. First, as implemented, risk assessment is done opportunistically when patients consult a health facility. This may do little to bring exposure to heightened CVD risk to the attention of the vast majority of people who are unaware of their hypertension, diabetes or dyslipidemia. To go below the tip of the iceberg of CVD risks, it may be

¹ There is: i) a low rate of awareness of hypertension among those diagnosed by survey measurements; ii) a low rate of medication of those diagnosed as hypertensive; and, iii) a low rate of blood pressure control among those under medication.

² WHO guidelines propose a hybrid approach of treating individuals with elevated risk indicated by a probability of a CVD event within 10 years according to the WHO/ISH charts in excess of a threshold (e.g. 30%) or high blood pressure (\geq 160/90 mmHg) or high blood cholesterol (total cholesterol \geq 8 mmol/dL) (WHO 2007). The CVD risk threshold can be determined by countries on the basis of resource availability.

necessary to combine the improved primary care offered in facilities with information that alerts individuals to their susceptibility to CVD and their potential to benefit from primary prevention. Without this, uptake of risk assessment and screening may be low.

Even if at-risk individuals do seek screening, the health impact could still be muted if implementation of the program is weak. Staff may lack the training and/or motivation to follow the protocol of risk assessment, screening, counselling and medication. Diagnostic equipment may not be available. Supplies of medication may be inadequate or sporadic. Without investment of resources necessary to cope with the demands on primary care facilities that can be expected to arise from higher rates of detection of CVD risk, adoption of the PEN may promise more than can be delivered.

While the PEN protocols specify treatments of proven cost-effectiveness, as far as we are aware, the package itself has not been evaluated as implemented in any country. Its effectiveness in delivering primary prevention of CVD and averting avoidable mortality has not been established. This gap in evidence is remarkable given the scale of the CVD burden in LMICs and widespread reliance on the PEN to reduce it.

This project aims to go some way towards filling the knowledge deficit by assessing the demand for and effect of primary prevention of CVD implemented through the PEN in the Philippines (PhilPEN). Its first objective is to establish the role of deficient information about CVD risks in discouraging healthy behaviour and constraining demand for primary prevention. Randomized provision of information on personal CVD risk based on measured risk factors will allow us to assess the extent to which perceived risks respond to such information and, consequently, how lifestyles and the demand for CVD screening and medication are affected.

The second objective is to evaluate the extent to which the PhilPEN program is successful in delivering effective primary prevention that reduces the risk of CVD. This will be done by randomly encouraging uptake of the program's risk screening and using this to trace the impact on exposure to risk factors, medication of hypertension and the predicted risk of CVD and awareness of this risk.

2. Setting

CVD is the main cause of death in the Philippines; 30% of deaths are attributable to cardiovascular conditions (WHO, 2012), which is close to the global average. While the CVD death rate in the Philippines is lower than in most LMICs in the Western Pacific, it is much higher than in neighbouring high-income countries. This is indicative of a great deal of avoidable mortality.

The high rate of CVD mortality in the Philippines, as elsewhere in developing Asia, is partly the consequence of high prevalence of associated risk factors: raised blood pressure at 22%, smoking at 25%, physical inactivity at 46%, overweight/obesity at 31% and borderline-high cholesterol at 47% (FNRI-DOST, 2015). However, these rates are not higher than those of the high-income countries in the region that have considerably lower CVD-related mortality (WHO, 2012). This suggests deficiencies in the prevention and control of CVD given exposure to risks. Like many LMICs, the Philippines faces a major health policy challenge: demographic and behavioural changes generate a heavy NCD burden before the health system has developed the universal, resilient and responsive primary care required to manage it.

The Philippines adopted its version of the PEN program in 2012 (Department of Health 2012a, 2012b). PhilPEN sets out a protocol for risk assessment and screening, lifestyle counselling and medication of hypertension and diabetes in all primary care facilities. From 2012, staff in Rural Health Units (RHU) and Urban Health Centers (UHC) began to be trained in operation of the protocol. By 2015, training was complete in 70% (78%) of municipalities (cities).

The PhilPEN protocol is the WHO protocol for the integrated management of diabetes and hypertension. The target population consists of individuals aged 25 years old and over with no established cardiovascular disease. The protocol consists of five actions.

- Risk assessment: Questions and measurements identify individuals as being at risk of CVD if they have at least one of the following characteristics: aged>40 years, smoker, overweight (BMI≥23), central adiposity (waist ≥ 90cm (male)/ 80cm (female)), raised blood pressure (≥120/80 mmHg), diabetes (reported diagnosis), family history of hypertension, stroke or heart attack, family history of diabetes or kidney disease. Some facilities conduct purposive risk assessment in the community. Most rely on opportunistic assessment when someone attends a RHU/CHC. The protocol requires that all individuals identified as 'at risk' continue to Action 2.
- 2) Risk screening: Questions are used to detect symptoms of angina, heart attack, stroke or transient ischemic attack (TIA), and measurements are taken of: a) blood lipids; b) urine protein; c) blood glucose (if has symptoms of diabetes but not diagnosed); and, d) urine ketones (if newly diagnosed with diabetes).
- 3) **Referral** to a higher level facility if: a) BP≥140/90 mmHg and aged<40 or already medicated with at least one drug; b) known heart disease, stroke, TIA, diabetes, kidney disease, angina, claudication or worsening heart failure; c) certain cases of high blood sugar; or d) any proteinuria.
- 4) **Prediction** of ten-year risk of fatal or non-fatal CVD event using World Health Organization/International Society of Hypertension (WHO/ISH) risk chart (with or without measure of cholesterol) for those not referred at Action 3.
- 5) **Treatment**: Both individual risk factors and the total CVD risk score are used in prescribing the treatment response (see Appendix A). Those exposed to particularly high risk through a single risk factor (hypertension, pre-existing CVD, high cholesterol and diabetes) should be prescribed the appropriate medication. Those with the CVD risk above 30% are to be given an antihypertensive if blood pressure is elevated and also a statin. Those with CVD risk 20-30% are to be given a low dose antihypertensive. Those with risk below 20%, as all others, are to be counselled on diet, physical activity and smoking cessation. The stipulated frequency of periodic follow-up depends on the risk score.

Department of Health (DOH) monitoring of PhilPEN implementation in six regions in 2015 revealed that not all facilities were following the protocol. Implementation requires that health facilities have sufficient supplies of medications, test devices and materials. The monitoring did not assess the availability of devices and materials at health centers but interviews conducted by the study team in Rizal and Pampanga provinces revealed that many RHUs are unable to perform blood tests and must refer patients to higher level facilities, which can result in the test not being undertaken.

PhilPEN was initially (2013) supported by DOH central procurement and distribution of drugs to RHUs under the Complete Treatment Packs (COMPACKs) program. In 2015, support for PhilPEN was shifted to the Maintenance Medicines Program and the Hypertension and Diabetes Clubs (H and D). Instead of the seven molecules for CVDs supplied under the COMPACK program, only four molecules are provided by the latter programs. Specifically, these programs are intended to make the anti-hypertensives (amlodipine, losartan, and metoprolol), as well as one diabetes medication (metformin), available at all RHU/CHCs at no charge irrespective of the patient's insurance cover or income. Statins are not supplied, despite the protocol stipulating that they should be given to all patients with a CVD risk in excess of 30% and to those with particularly high total cholesterol (≥ 8 mmol).

Allocation of the drug supply across facilities is demand based, although interviews conducted by the study team in selected RHUs reveal substantial delays in deliveries and possible stock-outs. There is substantial variation across facilities in the management of drug inventories. Some allow for potential shortages by admitting patients to the program only if a six-month supply of medication is secured in advance for that patient.

The study will be conducted in Nueva Ecija, a landlocked province of 2.15 million people in Central Luzon, which is one of the regions with the highest prevalence of major CVD risk factors, such as high blood glucose and smoking, in the country (FNRI-DOST, 2015). The province of Nueva Ecija is chosen because of its relatively high rate of poverty (29.6% compared with national average of 26.3% in 2015) despite being reasonably accessible from Metro Manilla (180 km). A high prevalence of poverty is important since the study aims to induce utilization of preventive care at RHU/CHCs, which mainly serve the poorer population. The vast majority of the population (83%) is rural dwelling.

3. Research objectives, questions and hypotheses

3.1 Objectives

Broadly, the project has two objectives. First, it seeks to further understanding of how beliefs about CVD risks affect health lifestyles and the demand for preventive care. Second, it aims to establish the effectiveness of the PhilPEN program in delivering primary prevention of CVD. The first objective has a scientific motivation of advancing knowledge of the formation of health beliefs. But it also derives from the practical need to raise demand for primary prevention if the burden of CVD on population health is to be lightened. Not only will we measure the accuracy of beliefs about exposure to CVD risk, but by randomly providing information on personal CVD risk, we will assess the extent to which biased beliefs constrain demand for primary prevention and sustain unhealthy lifestyles. In addition, we will test whether beliefs about susceptibility to CVD are responsive to the receipt of information on personal risk.

The second objective is more immediately motivated by policy. Implementation research on the PEN program is lacking. To the best of our knowledge, this will be the first study to establish whether the program as it is implemented is effective in delivering primary prevention of CVD.

Meeting both objectives will allow us to distinguish between possible scenarios. One is that PhilPEN is effective in preventing CVD of patients who access it but that its impact on population health is muted because poor information on susceptibility to CVD reduces the demand for primary prevention. Another is that even if improved information is effective in raising this demand, it will have little impact on population health through PhilPEN because of deficiencies in the operation of the program in health facilities.

Beliefs, information and health behaviour

The gross under-diagnosis of hypertension and diabetes suggests that improving awareness of risk factors is central to reducing CVD morbidity and mortality. Inadequate medication of these conditions is likely attributable, in large part, to lack of availability and affordability of medicines. But it could also stem from under appreciation of the risks of untreated, asymptomatic conditions, as well as the effectiveness of pharmacotherapies in preventing the progression from risk factor exposure to disease. Lack of appreciation of the long term gains from treating a condition that does not currently cause discomfort likely contributes to poor adherence to medication and lack of control of hypertension.

Central to these explanations for low awareness, medication and control of hypertension, diabetes and other CVD risk factors are beliefs about susceptibility to health risks, severity of consequent health conditions and effectiveness of medication in containing illness. According to the *health beliefs model* (Rosenstock 1966) providing individuals with information on their risk of developing CVD and counselling on actions to avert or manage the risk will lead to adoption of healthier lifestyles and uptake of effective screening and medication. But this may be overly simplistic. Without sufficient knowledge of the epidemiology of CVD, behaviour may change little in response to information about exposure to risk factors that do not immediately manifest in health problems. A negative result from a screening test could even encourage unhealthy habits that take time to have physiological effects. Bad news from a screening test that the risk is higher than had been anticipated may be filtered out by optimistically biased individuals wishing to avoid the distress aroused by contemplation of life-threatening disease (Sharot & Garrett 2016). Understanding how individuals respond to information on CVD risks is critical to designing programs that are effective in managing those risks.

We will elicit perceptions of CVD risk alongside the collection of data on health and behaviours related to CVD, including utilization of preventive care. These data combined with the randomized provision of information on personal CVD risk will allow us to identify the impact of information on lifestyles, preventive care and intermediate health outcomes and how it operates through beliefs about susceptibility to CVD. This goes beyond policy simulations that rely on assumptions about the impact of information on beliefs. For example, from the estimated impact of beliefs about HIV on sexual activity, Delevande and Kohler (2016) infer that policy should target beliefs. But that prescription is valid only if beliefs are responsive to information. We can test this.

If it is confirmed that beliefs about CVD risks do respond to the provision of information on those risks, then we can use the exogenous variation in risk perceptions induced by the experiment to estimate the causal effect of beliefs on behaviour. This overcomes a fundamental problem of the endogeneity of beliefs arising from their dependence on past behaviour (Paula et al 2014). The information intervention provides an instrument for beliefs that identifies their impact on choices.

The data on beliefs give us an important advantage over most studies of the impact of information. They allow the mechanism to be traced. Information programs are often found to be ineffective in changing health behaviour. Usually, it is not known whether this is because the information did not shift beliefs or because any change in beliefs did not feed through to behaviour. If this experiment also produces a negative result, we will be able to identify at what stage the *theory of change* failed.

Primary prevention of CVD through the PEN

The PEN is founded on a substantial body of evidence that establishes the effectiveness of behavioural change (smoking cessation, weight loss, physical activity and reduced intake of salt and fat) and medication in preventing CVD. It is known that quitting smoking and taking antihypertensives, for example, reduce the risk of heart attack. The difficulty lies not in knowing what to do for someone at risk of CVD. Rather, it lies in identifying who is at risk and ensuring that they get the interventions that are known to be effective.

The PEN relies on the WHO/ISH charts to identify those at elevated risk of CVD. These charts are not based on sound, verifiable statistical methods. Studies that assessed their external validity find very poor performance (Selvarajah et al 2014). The standard procedure for constructing a CVD risk prediction algorithm is to estimate a model for CVD events as a function of previously measured risk factors in a cohort followed over time. This method was not adopted to construct the WHO/ISH charts. The method by which they were derived is rather opaque. Risk factor prevalence estimates for each of the six WHO

regions were obtained from the WHO Collaborative Risk Assessment Project (WHO 2007), absolute CVD risks were taken from the Global Burden of Disease study and each coefficient representing the impact of a risk factor on the 10-year risk of a CVD event was taken from a separate published study.

Kariuki et al (2013) evaluate the performance of the WHO/ISH charts against criteria for a clinically useful CVD risk assessment (Cooney et al, 2009). The algorithm is found lacking with respect to representativeness of sample (which is entirely lacking), appropriateness of statistical methods (not specified) and checks on internal and external validity (not conducted). Selvarajah et al (2014) demonstrate that even the chart that makes use of information on cholesterol performs poorly in predicting CVD risks in the Malaysian population, with gross underestimation of risk. Despite the study sample having high prevalence of risk factors, the WHO/ISH risk chart placed 90% in the low-risk category (10-year CVD risk <10%), while the non-laboratory Framingham algorithm (D'Agostino, 2008), which uses BMI instead of cholesterol, categorized only 48% as low risk. The WHO/ISH chart placed only 3% in a high-risk category (10-year CVD risk >30%), while Framingham placed 23% in this category (10-year CVD risk \geq 20%). In addition to low agreement on risk categorization, there was low correlation between WHO/ISH and both the Framingham and the SCORE algorithms. The low correlation was due to the WHO/ISH charts placing many at low risk that the other two algorithms classified as high. The tendency for WHO/ISH charts to categorize the vast majority in the low risk category despite high prevalence of CVD risk factors has been demonstrated for Cambodia (97%) (Dugee et al 2013), Cuba (90%) (Nordet et al 2013), Jamaica (89%) (Tullock-Reid et al 2013) and Mongolia (94%) (Dugee et al 2013). Accuracy of the charts, particularly whether the risk classification is sufficiently detailed for medium to high risks, has been questioned (Persson et al 2003; Yikona et al 2002).

The apparent downward bias in risk prediction using the WHO/ISH charts means that the PEN, in the Philippines and elsewhere, may well be failing to deliver primary prevention of CVD to many who could benefit from it. One objective of this study is to examine whether this is indeed the case.

More specific to the Philippines, lack of resources and incentives for implementation of the PEN may have reduced its effectiveness there. Beyond the supply of some medicines and the training of staff, health facilities did not receive any increase in their budgets from the Department of Health (DOH) to support the implementation of PhilPEN. This, the lack of provision of some medications, the uncertain supply of other medications, the inability of some facilities to conduct all the required tests and the evidence from monitoring that the protocol is not being followed in all facilities, all suggest that the impact on population health may fall well short of the potential impact of a more effectively implemented program. One goal of this study is to establish the effectiveness of the PEN as it is actually implemented in the Philippines. This is more relevant than examination of a perfectly implemented program, since the medications and lifestyle changes prescribed by such a program have already been proven to be highly effective in the primary prevention of CVD. The question is whether such interventions are being implemented.

Since few health facilities are conducting risk assessment in the community, many who could benefit from primary CVD prevention may not be getting it. We will induce individuals to attend facilities for risk assessment and use this variation to evaluate the effectiveness with which the PhilPEN protocol is being implemented.

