[H3d] Updating of beliefs is asymmetrical in response to positive information, i.e. $prior_i > predicted_i$, and negative information i.e. $prior_i < predicted_i$.

Test:

• We run the following regression:

$$\begin{array}{l} (posterior_{i} - prior_{i}) = \lambda_{1i}(predicted_{i} - prior_{i}) \times 1(predicted_{i} \leq prior_{i}) + \lambda_{2i}(predicted_{i} - prior_{i}) \times 1(predicted_{i} > prior_{i}) + \varepsilon_{i} \end{array}$$

and test $\lambda_{1i} = \lambda_{2i}$ against $\lambda_{1i} > \lambda_{2i}$. That is, under the alternative hypothesis, individuals who receive good news respond more than those who receive bad news. Such asymmetric updating is

consistent with the reinforcement of optimism bias. However, in light of Harris and Hahn (2011) and Shah et al. (2016), we cannot infer a mechanism for optimism bias from $\lambda_{1i} > \lambda_{2i}$ alone.

Q4: Do beliefs about susceptibility to CVD affect behavior in relation to lifestyles and the demand for preventive care?

[H4a] Beliefs play an important role in determining health behavior. Individuals are forward-looking and take into account their perceived susceptibility to CVD in deciding on their use of primary prevention and health lifestyles. Further, they use perceptions of the response of CVD risk to risk factors when deciding whether to change health habits such as smoking and diet/exercise.

Test:

- Run regressions of the form, y_i = βx_i + θp̂_i + ε_i, where the dependent variable is an indicator of a) whether the person has attended a health facility for a checkup, including blood pressure measurement and diagnostic tests, b) whether is taking medication for hypertension/diabetes, c) smoking (at all and intensity), d) BMI, e) exercise and possibly others. In one set of regressions, p̂_i will be the predicted value of the perceived personal CVD risk, which will be obtained from of one of the regressions described under [H3a]. That is, in the first stage, perceived personal CVD risk measured after the giving the treatment group information on the base rate and their predicted personal risk is regressed on the treatment group indicator. The IV estimate of θ tells us how behaviour responds to changes in CVD risk perceptions induced by information on those risks.

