- The regression model described in the preceding paragraph is possibly incorrectly specified. It supposes that an individual chooses her health behaviour in response to her perceived level of CVD risk. Logically, behaviour is determined by perceptions of how CVD risk varies with that behaviour. To test this model of rational behaviour, in the regressions described in the previous paragraph, we will replace the perception of personal CVD risk with the difference between this and the perception of what the CVD risk would be if the individual were to reduce her modifiable risk factors. This difference in risk perceptions will be instrumented by regressing it on the treatment group indicator.

Q5: Does the demand for preventive care and health behavior, and ultimately CVD risk, respond to information on current CVD risk?

[H5a] Receiving information on the predicted 10-year CVD risk (including information on the base rate and the risk conditional on reduced exposure to risk factors) affects the demand for primary prevention and lifestyles related to CVD risk. As a result, the provision of information reduces CVD risk.

Test:

- Repeat the regressions described in [H4a] but replace the perceived risk with I_i indicating whether the individual was in the information treatment group. That is, estimate the reduced form effect of the information intervention on behaviour.
- Run the same sort of regression but with the dependent variable being predicted CVD risk at follow-up and conditioning on predicted CVD risk at baseline. If the information intervention has

succeeded in reducing risk factors (blood pressure, smoking and BMI) either through utilization of preventive care or directly through lifestyles, then the mean CVD risk score of the information treatment group will fall relative to that of the control group.

[H5b] Receipt of information on CVD risks affects behaviour not only through the correction of biased beliefs but also by reducing intrinsic uncertainty and increasing confidence in beliefs.

Elaboration

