Finally, a treatment group respondent will receive information on what the 10-year CVD risk would be for someone of the same age and gender who did not smoke, and had normal blood pressure and BMI. This will be presented as the optimal risk that could be achieved through primary prevention. If the respondent's risk is above the optimal, then they will be told the reason(s) for this - smoking, above a healthy weight or blood pressure reading is above normal. And the respondent will be told how the risk could be reduced – quit smoking, lose weight, get blood pressure down by taking medication, exercising, losing weight, eating less salt and fat. If the respondent's risk is not above the optimal, then they will be congratulated and advised how to keep the risk low.

CVD risk prediction algorithm

We have several reasons for not using the WHO/ISH risk charts to predict 10-year CVD risk, despite their use in PhilPEN. First, there are the methodological weaknesses of these charts identified in Section 2. They appear to produce downwardly biased predictions of CVD risk, which would result in less variation within the treatment group in the information on CVD risk provided. Besides providing inaccurate information and missing much of the variation in actual risk, we would need a much larger sample size in order to identify the effect of the intervention. It would hardly be worthwhile to randomize to a treatment if there is no variation in that treatment for 90% of the treated.

Further, the WHO/ISH charts only allow categorization of individuals into five ranges of CVD risk. They do not provide a point estimate of the CVD risk for each individual. This would have two drawbacks for our study. First, it would further limit the variation in the information we would be able to provide in the intervention. Second, it would not allow us to test the extent to which individuals use the information provided to update their reported estimate of the CVD risk.

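### H4a's instrumental-variable estimate is not identified as a causal effect of beliefs under the plan's own hypotheses, because the information arm is also expected to change behaviour by other routes

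*Combined protocol and SAP*

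**What the plan says.** Section 3.1 (Beliefs, information and health behaviour) first makes the step conditional on beliefs responding to information, then concludes: "The information intervention provides an instrument for beliefs that identifies their impact on choices".

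Section 3.2, H4a, implements this twice.

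- **Model 1.** Perceived personal risk after "information on the base rate and their predicted personal risk is regressed on the treatment group indicator". The resulting coefficient is said to show "how behaviour responds to changes in CVD risk perceptions induced by information on those risks".
- **Model 2.** The plan concedes that "The regression model described in the preceding paragraph is possibly incorrectly specified" and substitutes the perceived gain from reducing risk factors. The instrument stays the same: "This difference in risk perceptions will be instrumented by regressing it on the treatment group indicator".

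Elsewhere the plan describes other ways in which the same intervention may work.

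- H5b hypothesises that information "affects behaviour not only through the correction of biased beliefs but also by reducing intrinsic uncertainty and increasing confidence in beliefs".
- Section 5.2, on respondents above their optimal risk: "And the respondent will be told how the risk could be reduced".
- Section 7 (Knowledge of CVD risk factors) expects that the intervention may improve knowledge of causes.

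H3d and H5b separate respondents told that their risk is above their own estimate from those told that it is at or below it. That split is used in the updating and reduced-form regressions, not in the H4a instrumental-variable (IV) models. A weak-instrument test is stated only for the lottery (H6b).

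**The concern.** Each H4a model has one endogenous belief and one instrument, so it is just-identified and no overidentification test can reveal a failure. The coefficient is a causal effect of beliefs only if assignment changes behaviour solely through the instrumented belief (exclusion). If the effect differs between people, assignment must also move that belief in one direction for everyone (monotonicity). The plan states neither assumption for this instrument, and its own hypotheses contradict the first.

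At stake is the first study objective: whether the trial can report how far CVD risk beliefs drive lifestyle and preventive care, as distinct from whether giving information does.

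**Working it through.** **1. Exclusion, from the text.** Table 1 and section 5.2 give the order in the information arm: base rate, prior, personal risk, posterior (section F), then optimal risk with reasons and advice (section G). Model 1 instruments the section F belief. Whatever the later advice does to behaviour therefore lies outside the instrumented variable. The confidence route in H5b is by its own wording additional to the correction of beliefs, and applies to both models. H6a declines to use information as an instrument for checkups because beliefs can act on behaviour without contact with a facility. The same reasoning is not applied to H4a.

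**2. Sample available to H4a.** The inputs from section 10.1 are alpha 5% (taken as two-sided), power 80%, effect 0.2 SD, compliance 0.6, autocorrelation 0.6, ICC 0.1 and cluster size 10. The design effect is 1 + 9 × 0.1 = 1.9.

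- Control or lottery n = 2 × (1.96 + 0.84)² × (1 − 0.36) × 1.9 / (0.2 × 0.6)² ≈ 1,326. Table 6 has 1,306 to 1,361 across its columns.
- Information n = control n / (2/0.36 − 1). From the adopted binary column, 1,361 / 4.556 = 298.8, which is Table 6's 299.

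The plan gives no figure for the H4a IV itself.

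**3. First-stage strength.** The documents give neither the SD of perceived risk nor the mean shift, and section 7 says that power inputs for the belief outcomes are lacking. I assume SDs of 15, 20 and 25 points and an ICC of 0.1.

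SE = SD × √[1.9 × (1/299 + 1/1,361)] = SD × 0.0880, and F = (net shift / SE)².

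| Assumed SD | SE | F at a net shift of 2 points | Net shift needed for F = 10 |
|---|---|---|---|
| 15 | 1.32 | 2.3 | 4.2 |
| 20 | 1.76 | 1.3 | 5.6 |
| 25 | 2.20 | 0.8 | 7.0 |

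The 2-point shift is an illustration only. At ICC 0.05, F = 10 needs 3.6, 4.9 and 6.1 points.

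**4. Sign of the estimate.** All values in this step are assumed. A share q of respondents revises up by 10 points and the rest down by 10. Per 10 points, the effects on the probability of a checkup are t_u (up group) and t_d (down group). A direct effect d acts by any other route.

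IV = [q·t_u − (1 − q)·t_d + d] / [q − (1 − q)]

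- *Exclusion holds, equal effects* (t_u = t_d = 0.05, d = 0): IV = 0.05 at every q except 0.5, where it is undefined.
- *Direct effect d = 0.05*: at q = 0.4, (0.02 − 0.03 + 0.05)/(−0.2) = −0.20. At q = 0.3, 0.03/(−0.4) = −0.075. At q = 0.6, 0.06/0.2 = +0.30. At q = 1 there is no opposite movement, and IV = 0.05 + 0.05 = 0.10, twice the true value.
- *No direct effect, unequal positive effects* (t_u = 0.10, t_d = 0.02): at q = 0.4, (0.04 − 0.012)/(−0.2) = −0.14.

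Opposite movement alone therefore shrinks the first stage without reversing the large-sample sign. A reversal needs a direct channel or unequal effects. A direct channel biases the estimate even when everyone moves the same way.

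**5. An alternative instrument.** Take information × (predicted minus perceived base rate from section B), with the information indicator and the gap as controls. Section B precedes all information in both arms. The indicator removes direct effects only if they do not vary with the gap. As a counterexample, assume moves of ±10 points, an effect of 0.01 SD per point, and a direct effect of 0.2 SD confined to the good-news group. The bad-news contrast is 0.1 and the good-news contrast is −0.1 + 0.2 = 0.1, so the interaction IV is (0.1 − 0.1)/20 = 0 although the true effect is positive.

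**The case against.** The strongest reply has four parts.

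- **The claim in section 3.1 is conditional on beliefs responding.** H3a regresses the post-information belief on the treatment indicator, which is in effect the H4a first stage, so a negligible shift would be seen. This stands in part. It would reveal a weak first stage, although no criterion is set. It says nothing about exclusion.
- **Two-way movement is not established.** H2c expects overestimated base rates and H2f expects optimism relative to base rates, so the net direction is open. If most respondents revise the same way, the first stage could be strong. This stands, and it is why the size is given only as a range.
- **Model 2 uses the belief that the section G information targets,** and the up and down groups in H3d and H5b concern the level of risk. This also stands: no text shows the perceived reduction moving both ways. The confidence and knowledge routes still apply to model 2.
- **H4a is a mechanism analysis.** H5a already gives the reduced form, and H5b examines the competing channel. That limits the consequence, but support for H5b would itself undermine the causal reading of H4a, and the plan does not say so.

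**Conclusion.** The concern holds for exclusion. Under the plan's own hypotheses, the H4a estimate is not identified as a causal effect of beliefs in either model. This rests on the text alone. The extra channels are hypotheses and not findings, so the right response is to make the claim conditional rather than abandon the analysis.

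A reader might go further and infer that monotonicity fails, that the first stage will be near zero, or that the estimate will have the wrong sign. The documents do not support that. They give no distribution of priors, belief SD, mean shift or direct effect. Low F values follow only from an assumed small net shift, and a reversed sign only from an assumed direct channel or unequal effects. What can be said is conditional: at 299 v 1,361 with design effect 1.9, a net shift below about 4.2–7.0 points (SD 15–25) leaves F under 10, and a wrong sign is then possible.

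Nor does the point reach the principal outcome or the H5a comparison, neither of which uses this instrument.

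**What to change.** 1. In section 3.1 and H4a, replace the claim of identification with one conditional on exclusion and monotonicity. State that support for H5b would rule out a causal reading of the IV based on the indicator alone.
2. Present H5a as the randomised result, with the up/down split. Define the split identically in both arms from section B. The information arm's section D prior follows the base-rate information, and H5b as written compares treated subgroups with an unsplit control group.
3. Apply the weak-instrument test of H6b to both H4a first stages, and report weak-instrument-robust intervals.
4. Add, as a sensitivity analysis only, the IV using information × section B gap, controlling for the indicator and the gap. State that it removes direct effects only if they do not vary with the gap. H5b, which looks for the confidence effect among those given good news, and section 5.2, which varies the advice by risk profile, put that in doubt. The section B gap is also only a proxy for the gap in personal risk.

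The cost is a weaker headline claim and a little more analysis. The data are already in the planned survey, and the sample size and fieldwork do not change.
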